#### **2.4.5.1 Analyses of adverse events**

##### **Generalities**

The primary focus of adverse event (AE) reporting will be on treatment-emergent adverse events (TEAEs). Pre-treatment and post-treatment adverse events will be described separately.

If an adverse event date/time of onset (occurrence, worsening, or becoming serious) is incomplete, an imputation algorithm will be used to classify the adverse event as pretreatment, treatment-emergent, or post-treatment. The algorithm for imputing date/time of onset will be conservative and will classify an adverse event as treatment emergent unless there is definitive information to determine it is pretreatment or post-treatment. Details on classification of adverse events with missing or partial onset dates are provided in [Section 2.5.3](#).

Adverse event incidence tables will present by SOC, HLT, HLT, and PT, sorted in alphabetical order for each treatment group, the number (n) and percentage (%) of patients experiencing an adverse event. Multiple occurrences of the same event in the same patient will be counted only once in the tables within a treatment phase. The denominator for computation of percentages is the safety population within each treatment group.

Sorting within tables ensures the same presentation for the set of all adverse events within the observation period (pre-treatment, treatment-emergent, and post-treatment). For that purpose, the table of all treatment-emergent adverse events presented by SOC and PT sorted by the internationally agreed SOC order and decreasing frequency of PTs within SOCs will define the presentation order for all other tables unless otherwise specified. The tables of AEs by SOC, HLGT, HLT, and PT will be sorted by the SOC internationally agreed order and the other levels (HLGT, HLT, and PT) will be presented in alphabetical order, unless otherwise specified.

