8.1.2 Timing of administration

A training injection is planned on Week -1 (V2) with a placebo for alirocumab. A second training injection with placebo for alirocumab may be administered between Week -1 and randomization visit.

During the double-blind treatment period, alirocumab or placebo for alirocumab will be administered SC Q2W, starting at Week 0 continuing up to the last injection (Week 22) 2 weeks before the end of the DBTP. If the injection is scheduled to take place on the same date as the site visit, then the IMP should be administered after the blood sampling has been completed.

Further training with the scheduled double-blind alirocumab IMP can be done between W 0 and W 4 and at additional scheduled or unscheduled visits, as per investigator's judgment.

Double-blind IMP will start as soon as possible after the call for randomization using the treatment kit number provided by the IVRS/IWRS. The first injection after randomization will be done at the site by the patient or another designated person (such as spouse, relative, etc) under direct site staff supervision. Patients will be monitored at the investigational site for at least 30 minutes after this first double-blind injection.

Alirocumab IMP injection should be administered Q2W SC at approximately the same time of the day; however it is acceptable to have a window period of ± 3 days. The time of the day is based on patient's preference.

If by mistake or due to other circumstances an injection is delayed by more than 7 days or completely missed, then the patient should return to the original schedule of study treatment administration without administering delayed injections. On the other hand, if the delay is less than or equal to 7 days from the missed date, then the patient should administer the delayed injection and then resume the original schedule of study treatment administration.

Ezetimibe 10 mg or placebo for ezetimibe capsules will be taken orally once daily at approximately the same time of the day, with or without food. Preferably, on the injection days the IMP capsule will be administered roughly at the time of injection (either before or shortly after). The capsules must be taken until the day before the end-of-treatment visit (early or not), and not stopped at the time of the last injection.

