10.3.4 Handling of patients after permanent treatment discontinuation

Patients who prematurely discontinue study treatment (regardless of the reason) should still continue the study and undergo all visits and procedures as described in [Section 1.2](#) with the exception of study treatment administration and its associated procedures. At the time of treatment discontinuation, the patient should have, as soon as possible, an unscheduled visit with assessments normally planned at end of treatment visit (this should take place within 5 days of treatment discontinuation, if possible) and then resume the original study schedule until end of study (ie, follow up visit). In particular, in case of early treatment discontinuation before week 24, all efforts should be done to perform the week 12 and week 24 visits.

If after treatment discontinuation, the patient refuses to continue the study, then if possible, the patient should undergo an unscheduled visit with assessments normally planned at the end of treatment visit (it should take place within 5 days of treatment discontinuation, if possible). The patient, at a minimum, should then be followed up for at least 10 weeks from last study treatment administration or up to recovery or stabilization of any AE to be followed-up as specified in this protocol, whichever comes last. A final end of study visit can take place with assessments as specified in the end of study visit (ie, follow up visit) at 10 weeks after the premature treatment discontinuation.

All definitive discontinuation of study treatment should be recorded by the Investigator in the appropriate screens of the e-CRF and in the patient's medical records when considered as confirmed. IVRS/IWRS should be notified when a patient prematurely discontinues study treatment.

For patients randomized and not treated, all efforts should be made to perform the Week 12 and Week 24 visits in order to collect the laboratory data and at the least, the lipid parameters.

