### ***Observation period***

The period of safety observation starts from the time when the patient gives informed consent and is divided into the following periods:

- The PRE-TREATMENT period: defined as the time from the signed informed consent up to the first dose of double-blind IMP;
- The treatment-emergent adverse event (TEAE) period: defined as the time from the first dose of double-blind IMP up to the day of last dose of double-blind IMP injection+70 days (10 weeks) as residual effect of alirocumab is possible until 10 weeks after the discontinuation of double-blind IMP injection.

The TEAE period will include:

- The TREATMENT period defined as the time from the first dose of double-blind IMP up to the day of last dose of double-blind IMP injection + 21 days, as serum concentration of alirocumab is expected to be  $>10 \mu\text{g/mL}$  for approximately 21 days following administration of 150 mg, and because throughout the previous studies it was observed that when alirocumab concentrations declined below this concentration, decrease in effect on LDL-C is observed.
- The RESIDUAL TREATMENT defined as the time from the day of last dose of double-blind IMP injection + 22 days up to the day of last dose of double-blind IMP injection + 70 days (10 weeks).
- The POST-TREATMENT period: defined as the time starting the day after the end of the TEAE period (ie, 71 days after the day of last dose of double-blind IMP injection).

The on-study observation period is defined as the time from the day of first dose of double-blind IMP (capsule or injection, whichever comes first) until the last protocol planned visit of the patient. The last protocol planned visit is defined as the follow-up visit if done, or else 32 weeks after the randomization of the patient.

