### ***Analysis of pre-treatment and post-treatment adverse events***

- All pre-treatment AEs by primary SOC and PT, sorted by the internationally agreed SOC order and decreasing incidence of PTs (in the alirocumab group) within each SOC;
- All pre-treatment AEs leading to treatment discontinuation by primary SOC and PT, sorted by the sorting order defined above;
- All post-treatment AEs by primary SOC and PT, sorted by the internationally agreed SOC order and decreasing incidence of PTs (in the alirocumab group) within each SOC;
- All post-treatment SAEs by primary SOC and PT, sorted by the sorting order defined above.

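### The post-treatment AE and SAE percentages divide by the whole safety population, although completers have almost no post-treatment time, so they mix early stopping with AE risk

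*SAP*

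**What the plan says.** SAP 2.4.5.1 (Generalities) sets a single denominator for AE incidence tables: "The denominator for computation of percentages is the safety population within each treatment group". Protocol 11.4.3.1 has the same rule.

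Later in SAP 2.4.5.1, under pre-treatment and post-treatment adverse events, the plan lists "All post-treatment AEs by primary SOC and PT, sorted by the internationally agreed SOC order and decreasing incidence of PTs", followed by a matching table of post-treatment SAEs. Neither has its own denominator, a count of patients observed, or an adjustment for observation time.

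The timing comes from four places:

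- **Start of the period.** SAP 2.1.4 has the post-treatment period "defined as the time starting the day after the end of the TEAE period", that is, "71 days after the day of last dose of double-blind IMP injection".
- **Last injection.** Protocol 8.1.2 has injections "continuing up to the last injection (Week 22) 2 weeks before the end of the DBTP".
- **End of observation.** Protocol 10.1.3.1 puts the follow-up visit at Week 32 (Day 225, 7 days either side). Protocol 10.4.3 ends AE recording at that visit.
- **Early stoppers.** Under Protocol 10.3.4 they attend an unscheduled visit and then "resume the original study schedule until end of study (ie, follow up visit". Those who refuse to continue are followed for at least 10 weeks from the last dose.

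**The concern.** A percentage of the safety population is a fair summary when most of that population was observed in the period. Here most of it was not. Nearly all post-treatment time belongs to patients who stopped injections early and stayed in the study, while completers fill the denominator with little or no time in which an event could be recorded.

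Two misreadings become possible. If the arms differ in how many patients stop early, or when, the table can show a between-arm difference even though AE risk after stopping is the same. And a real risk among early stoppers can print as one or two percent and be read as negligible.

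**Working it through.** **1. The plan's own figure.** Week w falls on Day 1 + 7w.

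- Week 22: 1 + 154 = Day 155.
- End of the TEAE period for a completer: 155 + 70 = Day 225.
- Week 32: 1 + 224 = Day 225.

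This reproduces the statement in Protocol section 4 that follow-up ends 10 weeks after last dosing.

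**2. Post-treatment days for a patient seen on Day 225.** Days = 225 − (1 + 7w + 70) = 154 − 7w, where w is the week of the last injection.

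| Last injection | Post-treatment days |
|---|---|
| Week 0 | 154 |
| Week 4 | 126 |
| Week 12 | 70 |
| Week 20 | 14 |
| Week 22 (completer) | 0 |

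If early stoppers' last injections are spread evenly over Weeks 0 to 20 (assumed), the mean is 154 − 7 × 10 = 84 days.

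**3. Completers within the windows.** Take the last injection on Days 152 to 158 (3 days either side, Protocol 8.1.2) and the visit on Days 218 to 232, all 7 × 15 = 105 combinations equally likely (assumed). Days = max(0, visit − injection − 70).

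- Combinations with any post-treatment day: 10 + 9 + 8 + 7 + 6 + 5 + 4 = 49, and 49/105 = 46.7%.
- Mean: 210/105 = 2.0 days. Maximum: 10 days.

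**4. Whose time it is.** With means of 84 and 2.0 days and all stoppers staying, early stoppers supply:

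- at 5% early stopping, 0.05 × 84 / (0.05 × 84 + 0.95 × 2.0) = 4.2/6.1 = 69%;
- at 10%, 8.4/(8.4 + 1.8) = 82%.

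On nominal dates the share is 100%. It falls to 48% if only 3% stop early and 70% of those stay.

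**5. What the planned table prints.** Percentage = s·p_s + (1 − s)·p_c, where s is the early-stop share and p_s and p_c are the chances of an event in stoppers and completers. Assume a constant AE hazard h per 30 days, equal in both arms. For h = 0.05, 0.10 and 0.20, p_s = 12.8%, 23.6% and 40.3%.

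- Nominal dates (p_c = 0), h = 0.10: s = 3%, 5%, 10%, 15% prints 0.7%, 1.2%, 2.4%, 3.5%. The ratio for 10% versus 5% is 2.0.
- With windows, all stoppers staying, h = 0.10: 2.96% versus 1.81%, ratio 1.63. Over the three hazards the ratio is 1.60 to 1.65.
- With windows and 70% of stoppers staying: 1.51 to 1.57.
- For comparison, keep s at 5% and double the hazard, on nominal dates: 0.64% to 1.18% (ratio 1.84), or 1.18% to 2.02% (ratio 1.71).

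**6. A rate per patient-day.** Use 400:200, 10% versus 5% stopping, h = 0.10 per 30 days, and count all events.

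- Nominal dates: 40 × 84 = 3,360 patient-days and 11.2 expected events, against 10 × 84 = 840 and 2.8. Both give 0.33 per 100 patient-days, ratio 1.0.
- With windows, completers add 360 × 2.0 = 720 and 190 × 2.0 = 380 days. Expected events are 13.6 in 4,080 days and 4.07 in 1,220 days, again 0.33 in both arms.

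**7. Why a denominator of patients with at least one post-treatment day is not enough.** Assume 30% of stoppers have an event in both arms and no completer does.

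- 12/(40 + 0.467 × 360) = 12/208 = 5.8%.
- 3/(10 + 0.467 × 190) = 3/99 = 3.0%.

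The ratio is 1.9, hardly better than 2.0, because nearly half the completers enter with only a few days each.

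**The case against.** The strongest reply concerns weight. SAP 2.4.5.1 puts the primary focus on TEAEs, SAP 2.4.5 rules out formal testing, and the period starts only after the 10 weeks in which residual effect is expected. Counts are printed beside the percentages. SAP 2.2 tabulates discontinuation by arm and reason, plots it by Kaplan-Meier, and describes insufficient post-treatment follow-up. All of this stands and limits the point to two descriptive tables. It does not supply what is missing: how many patients were observed in the period, and for how long.

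A second reply is that confining attention to patients observed after day 70 conditions on stopping, a post-randomization event that AEs may themselves cause. The safety population at least keeps all treated patients. This also stands. A rate corrects for unequal observation time but does not restore a randomized comparison.

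The SAP's restriction of PCSA denominators to assessed patients is only a loose precedent, since AEs are recorded continuously. Closer support is the concern for differential exposure time in Protocol 11.4.3.1 and SAP 2.4.5.3.

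A reader might go further and infer that only early stoppers are observed, or that the tables measure early stopping more than AE risk. The documents do not support either. Within the windows, about 47% of completers could have some post-treatment time. Stoppers who refuse to continue may leave with about none. Protocol 6.2.1 extends the end of study for ongoing SAEs, AESIs or antibody titers at or above 240. No early-stop rate is given for either arm, and step 5 shows that doubling the hazard moves the percentage about as much as doubling the stop rate does.

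**Conclusion.** The point holds as a limited one. The timeline follows from the documents without assumptions: an on-schedule completer has zero post-treatment days, and an early stopper who stays has 14 to 154. The planned percentages are therefore diluted and combine each arm's share and timing of early stopping with AE risk, without showing either separately.

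The size of any between-arm distortion cannot be known from the documents. The ratios of about 2.0 (nominal dates) and 1.5 to 1.65 (windows) rest on assumed early-stop rates of 10% and 5%, a constant and equal hazard, and last injections spread evenly over Weeks 0 to 20. They illustrate the mechanism and do not predict a result. No efficacy conclusion and no TEAE table is affected.

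**What to change.** In SAP 2.4.5.1, for the post-treatment AE and SAE tables only:

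- keep the number of patients with events;
- add by arm the number of patients observed beyond last injection + 70 days and the total patient-days observed in that period;
- give the event rate per 100 patient-days as the between-arm summary, stating whether it counts all events or only first events with time cut at the event;
- footnote that completers have essentially no post-treatment time and that the comparison is of patients selected largely by early stopping.

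Do not rely on a denominator of patients with at least one post-treatment day alone.

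The cost is a few lines of SAP text and one derived variable, with no new data collection. The rates will be imprecise: at 5% early stopping, only about 20 of 400 and 10 of 200 patients would contribute substantial time. The comparison remains descriptive and non-randomized, and the rate removes the imbalance fully only if the hazard is roughly constant over the period.

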### ***Analysis of all treatment-emergent adverse events***

The following treatment-emergent adverse event summaries will be generated for the safety population.

- Overview of TEAEs, summarizing number (%) of patients with any
  - TEAE;
  - Serious TEAE;
  - TEAE leading to death;
  - TEAE leading to permanent treatment discontinuation;
- All TEAEs by primary SOC, HLGT, HLT, and PT, showing number (%) of patients with at least 1 TEAE sorted by the SOC internationally agreed order. The other levels (HLGT, HLT, PT) will be presented in alphabetical order;
- All TEAEs by primary SOC and PT, showing the number (%) of patients with at least 1 TEAE, sorted by the internationally agreed SOC order and by decreasing incidence of PTs within each SOC. This sorting order will be applied to all other tables, unless otherwise specified;
- All TEAEs by treatment group regardless of relationship in one column and, in the same table a second column with TEAEs related to alirocumab according to investigator's opinion by primary SOC, HLGT, HLT, and PT, sorted by the sorting order defined above;
- All TEAEs by maximal intensity (ie, mild, moderate, or severe), presented by primary SOC and PT, sorted by the sorting order defined above;
- Kaplan-Meier curves will be provided, when appropriate, for time from first dose of double-blind IMP (capsule or injection, whichever comes first) to the first occurrence of selected TEAEs. Patients without any event will be censored at the end of the TEAE period. Selected TEAEs could be local injection site reactions, general allergic reactions, hepatic disorders, diabetes among non-diabetic patients at baseline and TEAE related to any clinically significant signal that needs further characterization.

### ***Analysis of all treatment emergent serious adverse event(s)***

- All TEAEs by primary SOC, HLGT, HLT, and PT, showing the number (%) of patients with at least 1 serious TEAE, sorted by the internationally agreed SOC order. The other levels (HLGT, HLT, PT) will be presented in alphabetical order;
- All serious TEAEs by treatment group regardless of relationship in one column and, in the same table a second column with TEAEs related to alirocumab administration according to investigator's opinion, by primary SOC, HLGT, HLT, and PT.

### ***Analysis of all treatment-emergent adverse event(s) leading to treatment discontinuation***

- All TEAEs leading to treatment discontinuation, by primary SOC, HLGT, HLT, and PT.

### ***Analysis of groupings of adverse event(s) including selected adverse events of special interest***

- All grouping of TEAEs including adverse events of special interest as listed in [Section 2.1.4.1](#) will be analyzed using selections defined in [Section 2.1.4.1](#) and will be presented by SMQ and PT (when selection is based on SMQs) and by SOC and PT (when selection is based on the e-CRF tick box or HLGT/HLT). The summaries will be sorted by decreasing incidence of PT within each SOC/SMQ (in the alirocumab group).
- Analyses of grouping of AEs for diabetes will be performed overall and according to the diabetic status at baseline.

In addition, the following variables will be tabulated for the local injection site reactions TEAEs:

- Intensity of the event (mild, moderate, severe);
- Number of events divided by the number of double-blind IMP injections received;
- Time from first double-blind IMP injection to first injection site reaction;
- Description of the highest intensity of each symptom recorded in the specific e-CRF page with table and bar chart.

Besides, description of symptoms and possible etiologies for General Allergic Reaction TEAE reported by investigator (using the tick box), will be presented.

### ***Analysis of cardiovascular events***

Adjudication results of treatment-emergent CV events will be summarized on the safety population.

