10.1.3 Follow-Up Period

10.1.3.1 Follow-Up Visit (Visit 9/ Week 32/ Day 225 \pm 7)

- Collect AEs
- Record concomitant medication
- Get body weight measurement
- Take vital signs including HR and BP.
- Perform physical examination (only in case of clinically relevant abnormality at the end of treatment visit)
- IVRS/IWRS contact to document the end of study
- Urinalysis (only in case of clinically relevant abnormal value at the end of treatment visit)
- Urine pregnancy test (WOCBP only)
- Obtain fasting blood sample for:

- Anti-alirocumab antibodies (as per schedule note in study flowchart of [Section 1.2](#))
- Only in case of clinically relevant abnormal values for these parameters at the end of treatment visit will the following be obtained at this visit:
 - a) Hematology: CBC including RDW and reticulocyte count, hematocrit, Hb, red blood cell count, white blood cell count with differential blood count and platelet
 - b) Chemistry: glucose, sodium, potassium, chloride, bicarbonate, calcium, phosphorous, urea nitrogen, creatinine, uric acid, LDH, total protein, albumin and γ GT
 - c) HbA1c
 - d) Liver panel (ALT, AST, ALP, and total bilirubin)
 - e) CPK

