10.6.3 Cardiovascular events

The following suspected or confirmed cardiovascular events that occur from randomization until the follow-up visit, should have a corresponding specific eCRF pages ± adjudication package prepared (as per the site manual) and submitted to the CEC:

- MI
- Cerebrovascular events (eg, stroke, transient ischemic attack, intracranial bleeding, ischemia or bleeding of spine or retina)
- Unstable angina requiring an emergency room visit or requiring/prolonging hospitalization

- Congestive heart failure requiring an emergency room visit or requiring/prolonging hospitalization
- All coronary revascularization procedures (eg, PCI, CABG)
- All deaths (including CHD death)

All suspected or confirmed cardiovascular events should also be reported as SAEs. For coronary revascularization procedures, please note that a medical or surgical procedure should not be reported as an adverse event, but rather, the reason for the procedure should be reported as the adverse event term (eg, unstable angina leading to PCI should be reported as ‘unstable angina’ instead of ‘PCI’).

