11.4.3.1 Adverse events

Adverse event incidence tables will present by SOC (sorted by internationally agreed order), HLGT, HLT and PT sorted in alphabetical order for each treatment group, the number (n) and percentage (%) of patients experiencing an AE. Multiple occurrences of the same event in the same patient will be counted only once in the tables within a treatment phase. The denominator for computation of percentages is the safety population within each treatment group.

Adverse event incidence table will be provided by treatment group for all types of TEAEs: all TEAEs, all treatment emergent AESI (defined with a PT or a prespecified grouping), TEAE by maximal intensity, all treatment emergent SAEs and all TEAEs leading to permanent treatment discontinuation.

If any clinically significant signal is detected and need further characterization or for AE of clinical interest, exploration of time to onset will be performed for these selected TEAEs as described below to account for the differential exposure time in all patients.

Selected TEAEs will be also analyzed using time-to-event approach (Kaplan-Meier methodology). Time from the first dose of double-blind IMP injection to the first occurrence of

the event will be calculated (only the first event will be counted). Patients without any event will be censored at the end of the TEAE period.

Death: The following deaths summaries will be generated:

- Number (%) of patients who died by study period (TEAE, on-study, post-study) summarized on the safety population by treatment received
- Death in nonrandomized patients or randomized and not treated patients
- TEAE leading to death (death as an outcome on the AE CRF page as reported by the Investigator) by primary SOC, HLGT, HLT and PT showing number (%) of patients sorted by internationally agreed order of SOC and alphabetic order of HLGT, HLT, and PT.

Adjudicated cardiovascular events:

The number and percentage of patients experiencing a positively adjudicated CV event will be presented by treatment group overall and by category of adjudication.

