### ***Cardiovascular events***

Suspected CV events that occur from randomization until the follow up visit will be submitted to the Clinical Events Committee (CEC) for adjudication.

Adjudicated CV events include all CV AEs positively adjudicated as defined in the Clinical Events Committee charter. The following categories will be described:

- CHD death;
- Non-fatal MI;
- Fatal and non-fatal ischemic stroke;
- Unstable angina requiring hospitalization;
- Congestive heart failure requiring hospitalization;
- Ischemia driven coronary revascularization procedure.

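### Non-fatal cardiovascular events occurring more than 70 days after the last injection are adjudicated but appear in no planned table of adjudication results

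*SAP*

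**What the plan says.** **Collection.** Protocol 10.6.3 requires submission to the adjudication committee for "The following suspected or confirmed cardiovascular events that occur from randomization until the follow-up visit". SAP 2.1.4.1 agrees: "Suspected CV events that occur from randomization until the follow up visit will be submitted to the Clinical Events Committee (CEC) for adjudication". Neither ties adjudication to being on treatment. Under Protocol 10.3.4, patients who stop treatment early "should still continue the study and undergo all visits and procedures as described in" the flow chart, through to the follow-up visit.

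**Planned analysis in the protocol.** Protocol 11.4.3.1 states: "The number and percentage of patients experiencing a positively adjudicated CV event will be presented by treatment group overall and by category of adjudication". It sets no treatment-emergent limit.

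**Planned analysis in the SAP.** SAP 2.4.5.1 has one sentence: "Adjudication results of treatment-emergent CV events will be summarized on the safety population". Under SAP 2.1.4 the treatment-emergent period closes 70 days after the last double-blind injection. SAP 2.1.4.1 defines adjudicated CV events as all those positively adjudicated and lists six categories to be described, so the SAP's endpoint definition is wider than its analysis.

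**Declared changes.** SAP 1.5 reports no major departure from the protocol's statistical section, and SAP 1.6 lists nothing.

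**Other relevant tables.** SAP 2.4.5.1 also plans tables of post-treatment AEs and post-treatment SAEs by system organ class and preferred term. SAP 2.4.5.2 tabulates deaths on-study, on-treatment and post-study, with the adjudicated reason.

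**The concern.** The adjudication window and the reporting window differ, and the difference is not spread evenly over patients. Both windows end together for someone who takes every injection. They separate only when injections stop early, so the unreported adjudication results belong almost wholly to patients who discontinued. That group is unlikely to be a random sample of the trial.

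What is at stake is the completeness of a descriptive safety display in a high-CV-risk population for which a dedicated committee was set up. A reader of the report who takes the adjudicated-event table to be the full yield of adjudication, as Protocol 11.4.3.1 implies, would be slightly wrong and would have no signal of it.

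**Working it through.** **1. The plan's own alignment.** Protocol Section 4 says the 8-week follow-up period ends 10 weeks after last dosing. Injections run from Week 0, "continuing up to the last injection (Week 22) 2 weeks before the end of the DBTP".
- Week 22 is Day 1 + 7 × 22 = Day 155.
- The treatment-emergent period ends on Day 155 + 70 = Day 225.
- The follow-up visit is Week 32, Day 225 (Protocol 10.1.3.1).

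The gap for an on-schedule completer is therefore 0 days, and the plan's figure reproduces. With the last injection 3 days early and the visit 7 days late, it is (225 + 7) − (152 + 70) = 10 days at most.

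**2. Gap for early discontinuers.** With L the study day of the last injection, gap = 225 − (L + 70).

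| Last injection | Day L | Treatment-emergent period ends | Gap to Day 225 |
|---|---|---|---|
| Week 0 | 1 | Day 71 | 154 days |
| Week 4 | 29 | Day 99 | 126 days |
| Week 8 | 57 | Day 127 | 98 days |
| Week 12 | 85 | Day 155 | 70 days |
| Week 16 | 113 | Day 183 | 42 days |
| Week 20 | 141 | Day 211 | 14 days |
| Week 22 | 155 | Day 225 | 0 days |

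The largest gap, Days 72 to 225, is 154/225 = 68% of the study period. If last injections fall evenly on the eleven dosing occasions from Week 0 to Week 20, the mean gap is (154 + 14)/2 = 84 days.

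**3. Expected number of events.** The documents give neither a discontinuation rate nor an event rate. Assume 5-15% discontinue, all are followed to Day 225, and adjudicated events occur at a constant 2-6 per 100 patient-years. With 600 patients:
- Unreported time, low: 600 × 0.05 × 84 / 365.25 = 6.9 patient-years; × 0.02 = 0.14 events.
- Unreported time, high: 600 × 0.15 × 84 / 365.25 = 20.7 patient-years; × 0.06 = 1.24 events.
- All time: 600 × 225 / 365.25 = 369.6 patient-years, giving 7.4 to 22.2 events.

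The unreported share of person-time is 6.9/369.6 = 1.9% to 20.7/369.6 = 5.6%. These figures lean high for two reasons. The event rate includes fatal events, which SAP 2.4.5.2 covers separately. Protocol 10.3.4 also lets a patient who refuses further participation have a final visit 10 weeks after stopping, so that patient's gap is close to zero.

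**4. Can the other tables supply the missing result?** For non-fatal events they cannot.
- The post-treatment AE and SAE tables use investigator diagnoses whatever the committee decided (Protocol 9.2.1, SAP 2.1.4.1). They mix positively and negatively adjudicated events.
- Protocol 10.6.3 has sites report the reason for a revascularization as the AE, not the procedure. The ischemia-driven revascularization category therefore cannot be recovered from preferred terms.
- A count of patients with any positively adjudicated event cannot be rebuilt from separate preferred-term rows.

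**The case against.** The strongest case on the other side has four parts.

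*The late events are reported.* Protocol 10.6.3 makes every suspected or confirmed CV event an SAE as well, and the SAP tabulates all post-treatment SAEs. Deaths carry their adjudicated cause on-study. Events in the first 70 days after the last injection are in the adjudicated summary. This stands. A reader might infer that adjudicated events in early discontinuers are in no table at all; the documents contradict that. Only the adjudication result for late non-fatal events is missing.

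*The restriction matches a stated focus.* The protocol synopsis names adjudicated CV events within the safety analysis and then says that analysis focuses on the treatment-emergent period; SAP 2.1.4 justifies the 70 days by possible residual effect. This explains why the treatment-emergent table should lead. It does not exclude other summaries: both documents report deaths beyond that period, and the SAP tabulates post-treatment AEs.

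*No inference is affected.* A reader might infer that a randomized comparison of CV events is compromised. No such comparison is planned. SAP 2.4.5 makes the safety summaries descriptive with no formal testing, and SAP 2.3.2 analyzes patients by treatment received. This stands in full.

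*The number is tiny.* Probably about one event or fewer. This stands too, and it sets the severity. Against it, with only some 7 to 22 events over six categories and two arms randomized 2:1, one omitted event can visibly change a category count.

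**Conclusion.** The point holds as an undeclared, minor presentation gap. The SAP's summary of adjudication results stops at last injection + 70 days, while adjudication continues to the follow-up visit and Protocol 11.4.3.1 sets no such limit. The gap follows from the documents' own dates: about 0 days for on-schedule completers and 14 to 154 days for early discontinuers who stay in follow-up. The estimate of 0.1 to 1.2 affected events rests on assumed discontinuation and event rates, an even spread of last injections and full follow-up to Day 225; none of these is given as a figure in the plan. Primary and key secondary efficacy conclusions are untouched.

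**What to change.** In SAP 2.4.5.1, keep the treatment-emergent summary and add one table of the number and percentage of patients with a positively adjudicated CV event, by treatment group, overall and by category, over the on-study observation period in SAP 2.1.4 (first dose to the follow-up visit, or 32 weeks after randomization if that visit is not done). This closes the gap for every treated patient and delivers what Protocol 11.4.3.1 describes. If the sponsor prefers the restriction, it should be stated and justified in SAP 1.5.

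The cost is one extra descriptive output. The events are already collected and adjudicated and the period is already defined, so no new data are needed.
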